4.9 Study Device Placement and Exposure

Study device placement and removal data will be summarized for the ITT and Safety population, respectively including the number of relevant and evaluable cycles with device use for subjects randomized to VeraCept. The study device placement and removal data will be presented in the listings.

4.9.1.1 Study Device Placement

The following parameters will be reported in the table for study device placement:

Number (%) of subjects who

- Attempted first insertion
 - Had successful first insertion
 - Failed first insertion
- Attempted second insertion after failed first insertion
 - Had successful second insertion
 - Failed second insertion
- Had medication during either attempt
- Required mechanical dilation in either attempt
- Number of cycles with device in place for Years 1, 2, 3, 4, 5 separately

4.9.1.2 Study Device Expulsion/Removal

The following parameters will be reported in the table for Years 1, 2, 3, 4, and 5 separately:

Number (%) of subjects who had study device removal

Number (%) of subjects who had study device expulsion

Number (%) of subjects with device expelled prior to the visit along with corresponding expulsion status (partial or complete)

Number (%) of subjects who had removal accomplished by pulling the strings without difficulty

Number (%) of subjects with each reason for difficulty of removal

Number (%) of subjects with medication given during the procedure.

4.10 Multiplicity Adjustment

There is no formal efficacy analysis contained in this SAP, and there is no need for multiplicity adjustment for type I error α .

4.11 Safety and Tolerability

Adverse events will be coded and classified by system organ class (SOC) and preferred term (PT) using the Medical Dictionary for Regulatory Activities (MedDRA) version 24.0. The summaries of AEs will be limited to TEAEs. Number (%) of subjects reporting AEs and SAEs will be summarized for the Safety population.

4.11.1 Brief Summary of Adverse Events

The number (%) of subjects reporting any of the following events during the study will be reported in the brief summary of AEs for the Safety population:

- AE
- AE related to study device
- AE related to study device placement/removal procedure
- SAE
- SAE related to study device placement/removal procedure
- AE leading to study device removal
- AE leading to study discontinuation
- AE leading to Death

4.11.2 Adverse Events by System Organ Class and Preferred Term

The incidence of Treatment-Emergent Adverse Events (TEAE) and SAEs will be summarized by MedDRA primary SOC and PT. The summary will include the total number and percentage of subjects reporting an AE within an SOC and/or PT.

The incidence of TEAEs by SOC and PT by maximum severity for the Safety population will be presented.

Incidence of TEAEs by SOC and PT by closest relationship to study device for the Safety population will be presented.

The incidence of TEAEs by SOC and PT by closest relationship to drug placement/removal procedure for the Safety population will be presented.

The incidence of Treatment-Emergent SAEs by SOC and PT by closest relationship to drug placement/removal procedure for the Safety population will be presented.

Incidence of TEAEs experienced by at least 10% of subjects by SOC and PT for the Safety population

Incidence of AESIs (pain during insertion, pelvic infection (Pelvic Inflammatory Disease or endometritis), expulsions and uterine perforations), which includes the following MedDRA preferred terms: abdominal pain, abdominal pain lower, abdominal pain upper, pelvic inflammatory disease, procedural pain, device expulsion, dysmenorrhea following IDU placement, dysmenorrhea-post-procedural, embedded device, insertion pain, intermittent dysmenorrhea, post procedural dysmenorrhea, uterine perforation, worsening of dysmenorrhea, endometritis, post procedural discomfort, pelvic discomfort and pelvic pain will be summarized for the Safety population.

Incidence of Allergy-Related AEs, based on Medical Monitor review, will be summarized by PT and relationship to study device will be presented in the Safety population.

4.11.3 Narratives of Deaths, Serious Adverse Events, and Other Significant Adverse Events

Narratives of deaths, SAEs, AESIs, pregnancies, allergic reactions occurring within 30 days of insertion and/or related to VeraCept will be provided in the relevant section of the CSR.

4.11.4 Adverse Events Listings

A complete subject listing of all AEs will be provided in Appendix 16.2 in the CSR. This listing will include treatment, AE verbatim term, MedDRA primary SOC and PT, the time of onset and cessation of the event relative to the first insertion of study device, duration of the AE, whether serious or not, severity, relationship to study device, action taken, and outcome. Treatment-emergent and non-treatment-emergent events will be listed separately.

In addition, separate listings of all SAEs, AEs related to study device, AEs related to study device placement/removal procedure, AEs leading to death, AEs leading to study device removal, AESIs, Allergy-Related AEs and AEs as primary reason for exiting study will be provided.

4.11.5 VeraCept Expulsion Rates

Cumulative VeraCept Expulsion Rates for Years 1 through 5 will be estimated via Kaplan-Meier method for the Safety population. The complementary log-log transformation will be used to construct 95% CIs.

VeraCept expulsion includes both total expulsion and partial expulsion. Total expulsion is defined as cases in which VeraCept is observed in the vagina, not shown in the uterus by ultrasound, or if the women confirmed expulsion. Partial expulsion cases are defined as when

VeraCept is visible in the cervical canal by gynecologic exam or ultrasound. If partially expelled VeraCept is removed, the removal will be considered an expulsion event for this analysis.

- Time to expulsion in cycles will be defined as time to total expulsion discovered or removal of the partially expelled VeraCept from the date of successful insertion
- Removal of VeraCept for any other reason will be censored at the removal cycle.
- If a subject discontinued because of pregnancy, the subject will be censored at the cycle of conception
- Lost-to-follow-up will be censored at the last cycle where VeraCept is in Situ, defined as the date the subject was deemed lost to follow-up as entered on the Study Exit Status CRF page.
- Those with VeraCept still in place for protection at the end of exposure period will be censored at the end of exposure period.

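### Safety SAP 4.11.5 counts partial expulsion as expulsion but dates it only at removal, so a documented partial expulsion can have no event time or a late one

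*SAP*

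**What the plan says.** Safety SAP 4.11.5 plans Kaplan-Meier cumulative expulsion rates for Years 1 to 5 in the Safety population, VeraCept only, with 95% confidence intervals on the complementary log-log scale.

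- **What counts.** "VeraCept expulsion includes both total expulsion and partial expulsion". A partial expulsion is a case in which "VeraCept is visible in the cervical canal by gynecologic exam or ultrasound". Removal is no part of that definition.
- **When it becomes an event.** "If partially expelled VeraCept is removed, the removal will be considered an expulsion event for this analysis".
- **Event time**, counted from successful insertion. "Time to expulsion in cycles will be defined as time to total expulsion discovered or removal of the partially expelled VeraCept".
- **Censoring.** Removals made for other reasons are censored in the cycle in which they happen. On pregnancy, the rule reads: "If a subject discontinued because of pregnancy, the subject will be censored at the cycle of conception". On devices that are kept, it reads: "Those with VeraCept still in place for protection at the end of exposure period will be censored at the end of exposure period". Women lost to follow-up are censored at the date on which they were deemed lost.

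Two other sections of the Safety SAP touch the same event. A note in 4.1.5 treats a removal made because of partial expulsion as an expulsion, and is silent on a partial expulsion left in place. Section 4.9.1.2 tabulates devices expelled before a visit by status, partial or complete, and sets no removal condition.

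**The concern.** The event definition is wider than the event-time rule. A total expulsion takes the date on which it is discovered. A partial expulsion is also something discovered, yet it takes the date of a later act, removal, and without that act it takes no date at all.

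Two consequences follow. A woman with a documented partial expulsion and no removal within the period meets the SAP's own definition of expulsion but contributes no event to the curve. A woman whose device is removed in a later cycle than the finding contributes an event that is dated late and may fall in the wrong reporting year. The same holds if a partial expulsion progresses and is dated when the total expulsion is discovered. Extension visits are six-monthly to Year 3 and annual after that, so this gap can span many cycles.

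At stake is the yearly cumulative expulsion rate, a safety figure that readers will take to include every total and partial expulsion.

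**Working it through.** The plan states no expulsion rate, and no sample size or precision based on expulsion, so there is no figure to reproduce. The event counts and dates below are illustrative assumptions.

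**Inputs**
- 20 VeraCept women planned (Safety SAP 3).
- 28-day cycles; Year 1 ends on day 364 (cycle 13), Year 2 on day 728 (cycle 26), Year 3 on day 1092 (cycle 39), Year 5 on day 1820 (cycle 65) (Safety SAP 4.1.5).
- Month 60 target day 1825 (Safety SAP 4.1.4), ±30 days (Protocol 6.1.6).
- VeraCept removal is a listed Month 60/Exit Visit procedure (Protocol 6.1.6), and early removals follow the same visit (Protocol 6.1.7).

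**Formulas.** Cumulative rate = 1 − ∏(1 − d/n), with d events among n at risk. Cycle = day/28, rounded up.

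**Step 1: which documented partial expulsions have no event time in the period**
- Loss to follow-up, or withdrawal without removal: no removal date exists.
- Conception before removal, with discontinuation for pregnancy: censored at the cycle of conception.
- Removal at Month 60 after the period ends. The visit window is 1825 ± 30 = days 1795 to 1855, and the period ends on day 1820. Even the target day lies outside: 1825/28 = 65.2, so cycle 66.

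**Step 2: an uncounted partial expulsion (20 women, no other loss)**
- No total and one partial: 0% under the timing rule; 1/20 = 5.0% (95% CI 0.7 to 30.5) if counted at documentation.
- One total and one partial: 5.0% (0.7 to 30.5) under the rule; 1 − (19/20)(18/19) = 10.0% (2.6 to 34.4) if counted.
- Two total and two partial: 10.0% (2.6 to 34.4) under the rule; 20.0% (8.0 to 44.9) if counted.
- If losses leave 15 or 12 at risk when the one partial occurs after one total: 1 − 0.95 × 14/15 = 11.3%, or 1 − 0.95 × 11/12 = 12.9%, against 5.0% under the rule.

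**Step 3: late dating across a year boundary.** One total expulsion in cycle 3; one partial found on day 350 (350/28 = 12.5, cycle 13) and removed on day 380 (380/28 = 13.6, cycle 14); no losses. The Year 1 rate is 5.0% dated at removal and 10.0% dated at finding. The Year 2 rate is 10.0% either way.

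**Step 4: late dating with losses in between.** One total expulsion in cycle 3; one partial found in cycle 20 and removed in cycle 27; four women censored in cycles 22 to 25.

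| Event date | Year 2 (cycle 26) | Year 3 (cycle 39) |
|---|---|---|
| At finding, 19 at risk | 10.0% | 10.0% |
| At removal, 20 − 1 − 4 = 15 at risk | 5.0% | 1 − 0.95 × 14/15 = 11.3% |

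The removal rule is lower at Year 2 and higher at Year 3. If losses left 12 at risk at removal, the later figure would be 12.9% against 10.0%.

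**Step 5: no effect.** If every partial expulsion is removed in the cycle in which it is found, both rules give the same curve.

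**The case against.** The strongest reply is that the gap is narrow and the rest is inference. Most of it stands as a limit on the point.

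- **Removal at exit.** A woman who keeps a partially expelled device and attends the Exit Visit has it removed, and 4.11.5 then makes that an event. This stands: many retained cases become late events rather than missing ones, and the uncounted cases are those in Step 1.
- **Censoring is not stated.** A reader might infer that the SAP orders unremoved partial expulsions to be censored. It does not say so. The rule for devices still in place is worded for devices in place for protection, and it is unclear whether a device in the cervical canal qualifies. Censoring is only what the listed rules apparently lead to.
- **Direction.** A reader might infer that the reported rate can only be too low. Step 4 shows otherwise.
- **Section 4.9.1.2.** A reader might see a contradiction between that table and the curve. The table does not define partial expulsion differently. The two could count different women, but the text does not show that they must.
- **Visibility elsewhere.** Expulsion is an adverse event of specific interest, with summaries, narratives and listings (4.1.7.3, 4.11.2 to 4.11.4), and all pelvic examination and ultrasound data are listed (4.11.9). The information is not lost, but the curve is not corrected by it.
- **Size.** Five points is one woman in 20, and the intervals overlap almost entirely. The shift is about one standard error at a 5% rate (√(0.05 × 0.95/20) = 4.9 points) and about 0.75 at 10% (√(0.10 × 0.90/20) = 6.7 points).

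One argument does not succeed. The removal sentence might be read only as keeping such removals from being censored as removals for another reason. Even so, the timing rule offers a partial expulsion no date other than removal.

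**Conclusion.** The point holds in a limited form. Within 4.11.5 the timing rule does not match the definition that it serves. This is more than missing detail, because following the rule as written can leave a documented partial expulsion out of the period or place it in a later cycle or year.

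Each uncounted partial lowers the cumulative rate by about 5 points with 20 women at risk, and by more when fewer remain. Late dating lowers the rate between finding and removal and can raise it afterwards. These sizes rest on assumed event counts, dates and losses. The documents do not say how often partial expulsions go unremoved or are removed late, and the effect is nil if none do.

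The estimate is descriptive and single-arm, with no formal testing. The primary pharmacokinetic comparison is untouched. Nothing here bears on how a partially expelled device should be managed clinically.

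**What to change.** In 4.11.5, define time to expulsion as time from successful insertion to first documentation of total or partial expulsion, whether or not the device is then removed, and state that this date takes precedence over the censoring rules. Align the note in 4.1.5 and the table in 4.9.1.2 to the same event and date. Keep removal of a partially expelled device as a reported detail. Settle this before the Year 5 database lock.

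The cost is SAP wording and a minor re-derivation of event dates from examination and ultrasound data that are already collected. Reported yearly rates may move slightly up or down. Because 4.1.5 also supplies the exposure cycles and event types for the Pearl Index, the same edit should say how the new date affects evaluable cycles and the seven-day conception window for these women.

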10. ON-TREATMENT PREGNANCY DETERMINATION AND FOLLOW UP

On-treatment suspected pregnancy will be confirmed with both a urine and serum pregnancy test. Pregnancies will be promptly confirmed and dated by ultrasound evaluation and medical assessment as needed. Presence or absence of the study drug will also be determined by ultrasound. Removal of the study drug, if in place, will be performed as deemed appropriate by the study physician and upon obtaining subject consent/assent (note: removal itself may be performed by another clinician, such as a nurse practitioner). Consideration of study drug removal should include the following standard of care criteria: If the subject has an intrauterine pregnancy in the first trimester and the study drug is seen to be in the uterine cavity or cervix on ultrasound, remove the study drug if the retrieval threads are visible. If the retrieval threads are not accessible, the IUD should remain in the uterus until delivery (abortion or term).

Subjects will be counseled and followed for at least 6-weeks post-delivery, and the clinical outcome will be recorded. Any infant abnormalities should be reported.

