4.1.5 Exposure Periods

The first exposure cycle starts on Day 1 of successful study device insertion. A full exposure cycle is comprised of 28 days. One woman-year comprises thirteen 28-day cycles. The following exposure periods are defined for analysis in terms of planned study days and study cycles to facilitate the efficacy and certain safety analyses.

Exposure Period	Study Day of Period Start (PSTDY)	Study Day of Period End (PENDY)
Year 1 (Cycle 1- Cycle 13)	1	364
Year 2 (Cycle 14-Cycle 26)	365	728
Year 3 (Cycle 27-Cycle 39)	729	1092
Year 4 (Cycle 40-Cycle 52)	1093	1456
Year 5 (Cycle 53-Cycle 65)	1457	1820
First 2 Years (Cycle 1-Cycle 26)	1	728
First 3 Years (Cycle 1-Cycle 39)	1	1092
First 4 Years (Cycle 1-Cycle 52)	1	1456
5 Years (Cycle 1-Cycle 65)	1	1820

Type of Events and Study Day During an Exposure Period

ETYPE	Event	Study Day of Event (EVTDY)
A	Expulsion	Study Day of Expulsion date
B	Expulsion followed by conception within 7 days	Study Day of Expulsion date
C	Removal	Study Day of Removal date
D	Removal followed by conception within 7 days	Study Day of Removal date
E	Pregnancy before expulsion	Study Day of Conception date
F	Pregnancy before removal	Study Day of Conception date
H	Lost to follow-up without pregnancy, expulsion, or removal	Study Day of Last Date Device in Situ
I	Complete period without pregnancy, expulsion, or removal	Study Day of Period End Date

Note: Removal due to partial expulsion will be treated as expulsion

Exposure Duration in Days (EXDUR):

if EVTDY-PSTDY>0 then EXDUR = min(EVTDY-PSTDY+1, PENDY-PSTDY+1);
 else EXDUR=.;

Exposure Duration in Cycles (NCYCF) = EXDUR/28

Number of Completed Cycles (NCYCC) = INT(NCYCF)

Number Relevant Cycles (NCYCR)

=NCYCC+1 if last partial cycle is \geq 23 days
 =NCYCC+1 if last partial cycle ETYPE is B, D, E, or F
 =NCYCC, otherwise.

Number of Evaluable Cycles (NCYCEV) =NCYCR

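### Safety SAP 4.11.5 drops an expulsion from the Kaplan-Meier estimate if it preceded conception but is first found at the pregnancy work-up

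*SAP*

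**What the plan says.** Safety SAP 4.11.5 sets the estimator: "Cumulative VeraCept Expulsion Rates for Years 1 through 5 will be estimated via Kaplan-Meier method for the Safety population". Its intervals are specified as follows: "The complementary log-log transformation will be used to construct 95% CIs".

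The same section defines total expulsion to include a device "not shown in the uterus by ultrasound, or if the women confirmed expulsion", without excluding pregnant women. A device seen in the cervical canal is a partial expulsion. Event time runs to discovery, or to removal if the expulsion is partial: "Time to expulsion in cycles will be defined as time to total expulsion discovered or removal of the partially expelled VeraCept".

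The pregnancy rule reads: "If a subject discontinued because of pregnancy, the subject will be censored at the cycle of conception". It carries no condition on where the device was.

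Three other places bear on this:

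- Protocol section 10, on suspected pregnancy: "Presence or absence of the study drug will also be determined by ultrasound".
- Safety SAP 4.1.5 has a separate event type B, "Expulsion followed by conception within 7 days", dated at the expulsion. Type A (expulsion) is also dated at the expulsion. Types E and F, where the pregnancy comes before the expulsion or removal, are dated at conception. Section 4.11.5 does not refer to these types.
- Safety SAP 4.9.1.2 tabulates by year, with no pregnancy censoring: "Number (%) of subjects who had study device expulsion".

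**The concern.** The event and the censoring run on different clocks. An expulsion is dated when someone finds it; a pregnancy exit is dated back to conception. If a device is lost unnoticed, the woman conceives, and the loss is found at the pregnancy ultrasound, discovery necessarily follows conception. Kaplan-Meier uses whichever time comes first, so she is censored and her expulsion does not enter the estimate.

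The documents make this sequence foreseeable. The study device is to be the sole contraception (protocol 4.1). After Day 57, visits with a string check are six-monthly to Month 36 and annual after that. Protocol 4.4 lists pregnancy among the reasons for discontinuation but not expulsion, so such a woman would plausibly be recorded as leaving for pregnancy.

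Expulsion is an AESI, and 4.11.5 gives the plan's only cumulative expulsion estimate with confidence intervals. The cases at risk of being dropped are expulsions that were followed by pregnancy.

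**Working it through.** **Inputs**

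- VeraCept arm: 20 (safety SAP section 3). This agrees with the sample-size text in 3.2: 12 evaluable per group and 40% unevaluable give 12/(1 − 0.40) = 20. The Safety population is all successful placements, so the actual number may differ.
- Expulsion rate: the documents give none, so there is no plan figure to reproduce. Assumed for Year 1: 0 to 3 expulsions found outside pregnancy (cycles 2, 4, 6) and 1 or 2 that preceded conception but were found through pregnancy (conception at cycles 8, 10).
- Other removals: assumed 0, or 4 censored at cycle 7.

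**Order of dates for the case in question**

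Expulsion (unnoticed) < conception < discovery at ultrasound. Event time under 4.11.5 is discovery; censoring time is conception. Conception is earlier, so the literal rule censors.

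**Size of one lost event**

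Let S be the Kaplan-Meier survival just before the conception cycle and r the number at risk. Coding the woman as an event at that cycle, not as censored, raises the cumulative rate by S/r. With k earlier expulsions and no earlier censoring, S = (20 − k)/20 and r = 20 − k, so S/r = 1/20 = 5.0 points whatever k is.

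**Worked example, k = 1**

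- Rule as written: 1 − 19/20 = 5.0%.
- Case counted: 1 − (19/20)(18/19) = 10.0%.

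For the interval, the Greenwood sum is G = Σ d/[r(r − d)] and the standard error on the complementary log-log scale is √G/|ln S|. The limits are 1 − S^exp(∓1.96·se).

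- One event: G = 1/(20·19) = 0.00263, se = 0.0513/0.0513 = 1.00, limits 0.7% to 30.5%.
- Two events: G = 1/(20·19) + 1/(19·18) = 0.00556, se = 0.0745/0.1054 = 0.707, limits 2.6% to 34.4%.

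**Year 1 results, N = 20, one pregnancy-discovered case, no other removals**

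| Other expulsions | Rule as written (95% CI) | Case counted (95% CI) |
|---|---|---|
| 0 | 0% (none) | 5.0% (0.7 to 30.5) |
| 1 | 5.0% (0.7 to 30.5) | 10.0% (2.6 to 34.4) |
| 2 | 10.0% (2.6 to 34.4) | 15.0% (5.1 to 39.6) |
| 3 | 15.0% (5.1 to 39.6) | 20.0% (8.0 to 44.9) |

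With 4 removals already censored, fewer women are at risk and one case is worth 6.2 to 6.5 points (for k = 0, 1/16 = 6.25%; for k = 3, 21.5% against 15.0%). Two such cases are worth 10.0 to 13.1 points. With no such case the two codings give identical results.

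**Direction**

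Recoding a censored woman as an event at the same or an earlier cycle adds a factor below 1 to the survival product and cannot raise any other factor. Any bias from the rule is therefore downward.

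**The case against.** The best defence is contextual. Section 4.11.5 first defines the event, with no exclusion for pregnant women, and the bullets then deal with women who did not have one. On that reading the pregnancy bullet covers only women without an expulsion, and what is missing is a sentence on precedence. The reading is possible, but the text does not say it. The removal bullet is expressly limited to removals other than those for partial expulsion; the pregnancy bullet has no such limit, and the two dates put censoring first.

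Several other points stand and limit the concern.

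- **A case may never occur.** Protocol 1.1 cites first-year success of 97.8 to 99.9% for copper IUDs. Applied to 20 women, as an assumption, that is 20 × 0.001 = 0.02 to 20 × 0.022 = 0.44 pregnancies of any kind in Year 1, and only some would follow an unnoticed expulsion. String checks at Days 8, 15, 22, 29 and 57 and at the later visits may find an expulsion first.
- **The event stays visible elsewhere.** The crude table in 4.9.1.2, the AESI summary (4.11.2), the listings and the narratives are not censored for pregnancy. A crude count and a censored estimator may also differ without contradiction.
- **Types E and F are handled consistently.** With the device in place at conception, ending follow-up there agrees with 4.1.5 and loses no earlier expulsion.
- **The estimate is descriptive and imprecise.** It is a single-arm safety figure in a PK study, and the two intervals in the worked example overlap almost entirely.

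**Conclusion.** The point holds in a conditional form. If an expulsion preceded conception, was first found at the pregnancy work-up, and the woman's exit reason is pregnancy, the stated rule censors her before her event and the Kaplan-Meier rate is understated. With 20 at risk the loss is about 5 points per case, or about 6.2 to 6.5 points if four others are already censored. All event counts are assumptions.

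A reader might infer more than the documents support:

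- **That the reported rate is understated in any event, or that such expulsions are never counted.** The bias needs a qualifying case, and only the Kaplan-Meier estimate is affected. An expulsion discovered before conception already has the earlier time.
- **That every expulsion in a woman who leaves pregnant is wrongly lost.** Type E is dated at conception and agrees with the censoring.
- **That the loss could be 1/12 = 8.3 points.** Twelve is the minimum number evaluable for PK. The Kaplan-Meier analysis uses the Safety population, and nothing in the plan makes 12 its number at risk.

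The change is still worth making. The case is foreseeable, the direction of error is known, and one lost event is large relative to an arm of 20.

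**What to change.** Replace the pregnancy bullet in safety SAP 4.11.5 with a rule in three parts:

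1. Device in situ at conception (event types E and F in 4.1.5): censor at the cycle of conception.
2. Evidence places the expulsion before conception (type B, or an earlier expulsion, type A): count an expulsion event whatever the exit reason. Date it at the recorded expulsion date or, if that is unknown, no later than the cycle of conception.
3. Order unknown (device absent, or in the cervical canal, at the pregnancy evaluation): state the primary handling in advance and add a sensitivity analysis that counts these cases as events.

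Part 3 should not simply treat every absent device as expelled by conception. That would misclassify a device lost after conception and conflict with type E.

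Reconcile the Kaplan-Meier event count with 4.9.1.2 and explain any difference in a footnote.

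The cost is SAP wording and one programming rule. The ultrasound check is already in protocol section 10, and safety SAP 4.11.9 already lists pelvic examination and ultrasound data. The expulsion rate may come out slightly less favourable.
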